### **Adverse Events of Special Interest**

It is highly unlikely that the ALICE app produces adverse events. We identified a number of possible adverse events that may occur while using the app and described possible methods to avoid these adverse events.

The following adverse events are of special interest and should be reported within the same timelines as SAEs:

#### **Clinical adverse events**

- Since stimuli are played from a personal smart device, stimuli may be too loud or uncomfortable despite the measures that have been taken e.g. setting the volume at a comfortable level.

#### **Privacy related adverse events**

- Risks related to data/server security

### **Mitigation of adverse events related to use of the ALICE app**

To avoid that a stimulus is presented too loud or that a stimulus sounds different to the client than expected several measures have been taken. Clients using the ALICE app are instructed to adjust the volume of the smart device at a comfortable level (not too loud, nor too quiet) before starting to use the app. The level that has been set by the client will determine the volume at which the training is done. The app will automatically adjust the volume of the smart device to this level every time the client opens the app. If the client tries to increase the volume of his/her device after the volume has been set at a comfortable level, a warning will appear and the client is instructed to go back to the page to set the volume at a comfortable level.

Clients will be instructed to not use the ALICE app for more than 45 minutes a day to avoid causing additional noise induced HI. Noise induced HI is caused by chronic and excessive exposure to hazardous levels of noise and is characterized by a reduced sensitivity (>20 dB HI or HL) in the 3-6 kHz range, with normal sensitivity at lower and higher frequencies. The extent of HI depends on the intensity of the noise and duration of noise exposure. According to the latest WHO guidelines a sound intensity over 80 dB that is listened to for more than 40 hours a week can cause noise induced HI. Clients will use the app for 15 to 30 minutes each day on average, which should not be long enough to cause an additional noise induced HI even at the maximum volume. This rule is defined in the instructions for use.

---

 Standards for safe listening systems: Situational Analysis. Geneva: World Health Organization and International Telecommunication Union, 2017.

([https://www.who.int/pbd/deafness/Monograph\\_on\\_situation\\_analysis\\_and\\_background\\_for\\_standards\\_for\\_safe\\_listening\\_systems.pdf](https://www.who.int/pbd/deafness/Monograph_on_situation_analysis_and_background_for_standards_for_safe_listening_systems.pdf))

 World report on hearing. Geneva: World Health Organization; 2021. Licence: CC BY-NC-SA 3.0 IGO. (file:///C:/Users/u0150004/Downloads/9789240020481-eng.pdf)

These risks and mitigations were investigated on effectiveness (see CEP and IB for more info)

#### **Mitigation of adverse events related to the use of the ALICE app in combination with personal devices**

Speech materials can be streamed directly to the clients' hearing aid or cochlear implant, can be played in free field or can be played through headphones.

If clients stream directly to their hearing aid, clients are instructed to use the pre-set hearing aid or cochlear implant settings as programmed by their hearing care professional. The signals pass through the same algorithm as for the normal microphone inputs, with the same maximum output as is used in the participants daily life.

Similar precautions are taken for clients who use the ALICE app without streaming option. Clients who use headphones, earbuds or speakers are instructed to only use CE marked devices with the use of the ALICE app and to pay extra attention when setting the volume of the ALICE app. The ALICE app cannot control the quality or possible malfunctioning of the headphones, earbuds or speakers used by the client. However, CE-marked smart devices (tablet or smartphone) ensure a safe output level (which is regulated by EU standard EN 50332 in Europe since 2013). Clients are instructed to not exceed the recommended maximum output level of their smart device.

Before clients take the ALICE app home to train their listening and communication skills, they will be given the opportunity to use the app together with their hearing care professional. During this session, they will be asked to indicate if any of the stimuli sound uncomfortable or if any of the stimuli are too loud. The hearing care professional will be available at any point if problems with the ALICE app occur.

#### **Mitigation of privacy related adverse events**

We confirm that the software has an inherent safe design and is developed taking into account all possible risks related to cybersecurity (ISO 14791 and MDCG 2019-16 - Guidance on Cybersecurity for medical devices) according to the CIA model.

All data is pseudomised and safely stored on the servers of the KUL. All GDPR regulations are followed.

A data management plan is filled out and the KUL safety measures are activated if a data leak would be reported.

In case a data breach would occur (for instance by personal error, e.g. Loss of smartphone), the KU Leuven Privacy Policy & Data Management Procedure is followed.

#### **3.5.14.2. Adverse Events that do not require reporting**

In general, the following should not be reported as AEs:

- Pre-existing conditions, including those found as a result of screening (these should be reported as medical history or concomitant illness).
- Pre-planned procedures, unless the condition for which the procedure was planned has worsened from the first trial-related activity after the subject has signed the informed consent.

The following events are commonly observed and are therefore not considered as adverse events for the purpose of the trial:

- All AEs or SAEs should be reported

---

 Standards for safe listening systems: Situational Analysis. Geneva: World Health Organization and International Telecommunication Union, 2017.

([https://www.who.int/pbd/deafness/Monograph\\_on\\_situation\\_analysis\\_and\\_background\\_for\\_standards\\_for\\_safe\\_listening\\_systems.pdf](https://www.who.int/pbd/deafness/Monograph_on_situation_analysis_and_background_for_standards_for_safe_listening_systems.pdf))

Although these events should not be reported to the Sponsor, these should be recorded in the patient's medical notes according to routine practice.

The following events not to be considered as SAEs are:

- Pre-planned hospitalisations unless the condition for which the hospitalisation was planned has worsened from the first trial-related activity after the subject has signed the informed consent.
- Hospitalisation as part of a standard procedure for protocol therapy administration. However, hospitalisation or prolonged hospitalisation for a complication of therapy administration will be reported as an SAE.
- Hospitalisation or prolongation of hospitalisation for technical, practical, or social reasons, in absence of an AE.

### 3.5.14.3. Recording and reporting of Adverse Events

Investigators will seek information on AEs during each patient contact. All events, whether reported by the patient or noted by trial staff, will be recorded in the patient's medical record and in the (e)CRF within a reasonable time after becoming aware. If available, the diagnosis should be reported on the AE form, rather than the individual signs or symptoms. If no diagnosis is available, the Investigator should record each sign and symptom as individual AEs using separate AE forms.

The following minimum information should be recorded for each AE:

- AE description
- start and stop date of the AE
- severity
- seriousness
- causality assessment to the Investigational Medical Device (IMD) and/or study procedures
- outcome
- what caused the AE
- possible solution

Possible adverse events that may occur during this study:

- The test used in the clinical protocol are standard clinical tests used in daily practice. These tests do not hold any risks for the participants in the study.
- Use of the training app can lead to a high cognitive load, which can result in feelings of fatigue.

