#### *Enrolment of clients*

- Clients who match the criteria, will receive a brief introduction about the study, which may or may not include the ALICE app. If they are interested to participate in the study, they will receive an information brochure about the study programme, in which a more detailed description is provided (details about the course of the study, the 2 visits (at 0 and 8 weeks), the duration of the study and their rights and responsibilities.) They will also be informed that they will be assigned randomly to one of the two groups.
- If clients agree to participate in the study they will sign an informed consent form.
- A complete list of clients who wish to participate for each investigational site is sent to the KU Leuven researchers at the end of the recruitment period.
- After being stratified by age clients will be randomly assigned to one of the two groups by a KU Leuven researcher using an automatic seed generator:
  - 1 group will receive the standard of care

- 1 group will receive the standard of care with additional support of the ALICE app

	Responsible	Accountable
Clients match the criteria	Local PI	KUL PI
Clients get a brief introduction about the app and the goals of the study; when interested they receive a detailed information brochure	Local PI	
Clients sign an Informed Consent	Local PI	KUL PI
Clients are enrolled in the study	Local PI	KUL PI
Allocation of groups and randomization	KUL PI	KUL PI

*The study program and test protocol*

- Onboarding procedure: once the clients are enrolled they will receive a standard onboarding procedure, which will be led by the local PI. Within this procedure following points/formalities will be discussed with their client:
  - The study programme/course of the study
  - Appointment schedule to perform the tests
  - Procedure to follow in case of change
  - Contact information in case of questions
  - Risk & Safety management (see safety section), with special attention to following procedures:
    - Procedure to control the loudness of the stimuli provided by the app
    - Procedure to follow to ensure safe data management (compliant with GDPR)
    - Procedure to follow in case of adverse events and/or device malfunction
    - Rights and responsibilities
- Installation of the app
  - Intended use of the app
  - Compatibility of the app with personal (streaming) devices,
  - Instruction to use the app
  - First installation and set-up of account
- Test protocol (see below and Fig. 4)

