#### Description of the design type of clinical investigation to be performed (e.g. comparative double-blind, parallel design, with or without a comparator group) with rationale for the choice

The study design is a randomized controlled clinical trial (RCT) which is the golden standard for ascertaining the efficacy and safety of a new treatment or intervention. The goal of the current RCT is to demonstrate the superiority of the supplementary use of the ALICE app, as a new intervention over the existing standard of care.

In this RCT two groups will be compared:

- (1) A group that receives the standard of care, which is defined as followed:
  - a. Persons with a moderate to profound HI who are provided with a hearing aid
- (2) A group that receives the standard of care, supplemented with the ALICE app, to be used as a home-based monitoring, training and counselling tool.

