### Primary and secondary endpoints, with rationale for their selection and measurement

The outcome measures that will be used as an endpoint to determine the clinical benefit of the ALICE app are:

- Clients - Effectiveness of the app is ensured
  - Enhanced outcome measures at the end of the hearing aid trial period (Primary)
    - Enhanced speech understanding in noise
    - Enhanced speech understanding in daily life
  - Increased knowledge of the consequences of HI (Secondary)
  - Increased satisfaction of care delivery (Secondary)
  - Increased habituation to hearing aids (Secondary)
    - Satisfaction with hearing aid
    - Duration of daily hearing aid use
- HCP - Effectiveness of the app is ensured
  - Enhanced care delivery (Secondary)
    - Reduced F2F time with HCP (reduction in time, appointments, hearing aid fittings, tests, ...)

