#### *Recruitment of clients*

- Local IPs will be responsible for the recruitment of patients. Before they start with recruiting they will be instructed with clear inclusion and exclusion criteria (see 3.5.6.3 Subjects)
- The number of clients that should be enrolled will be in the range of 20-30 for every investigator site
- To be able to recruit 120 first time hearing aid users, the recruitment period will be spread out from April 2023 to August 2024, employing a rolling start strategy.
- Enrolment of clients
- Clients who match the criteria, will receive a brief introduction about the study, which may or may not include the ALICE app. If they are interested to participate in the study, they will receive an information brochure about the study programme, in which a more detailed description is provided (details about the course of the study, the 3 visits, the duration of the study and their rights and responsibilities.) They will also be informed that they will be assigned randomly to one of the two groups.
- If clients agree to participate in the study they will sign an informed consent form.
- After being stratified by age clients will be randomly assigned to one of the two groups by a KU Leuven researcher using an automatic seed generator:
  - 1 group will receive the standard of care
  - 1 group will receive the standard of care with additional support of ALICE app

	Responsible	Accountable
Clients match the criteria	Local PI	KUL PI

Clients get a brief introduction about the app and the goals of the study; when interested they receive a detailed information brochure	Local PI	
Clients sign an Informed Consent	Local PI	KUL PI
Clients are enrolled in the study	Local PI	KUL PI
Allocation of groups and randomization	Local PI	KUL PI

*The study program and test protocol*

- Onboarding procedure: once the clients are enrolled they will receive a standard onboarding procedure, which will be led by the local PI. Within this procedure following points/formalities will be discussed with their client:
  - The study programme/course of the study
  - Appointment schedule to perform the tests
  - Procedure to follow in case of change
  - Contact information in case of questions
  - Risk & Safety management (see safety section), with special attention to following procedures:
    - Procedure to control the loudness of the stimuli provided by the app
    - Procedure to follow to ensure safe data management (compliant with GDPR)

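### AEs are sought at patient contacts, and contacts can differ between the groups, so recorded AE counts can differ without any effect of the app

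*Combined protocol and SAP*

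**What the plan says.** **AE enquiry.** Section 3.5.14.3 says that "Investigators will seek information on AEs during each patient contact". It continues: "All events, whether reported by the patient or noted by trial staff, will be recorded". The minimum data include the "start and stop date of the AE". No common question, recall period or enquiry schedule is set.

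**Shared visits.** The text describes one schedule per arm, without distinguishing the groups: two visits at 0 and 8 weeks in Arms 1 and 3 (3.5.6.2 and 3.5.6.4, Enrolment of clients), and in Arm 2 "the 3 visits, the duration of the study" (3.5.6.3, Recruitment of clients).

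**Contacts that can differ.**
- Before taking the app home, ALICE clients try it with their hearing care professional, and "they will be asked to indicate if any of the stimuli sound uncomfortable or if any of the stimuli are too loud" (3.5.14.1, mitigation for use with personal devices).
- The Project support text in the monitoring plan of each arm gives a route for app-related help. Only app users can need it.
- Arm 2 lists as a secondary endpoint "Reduced F2F time with HCP (reduction in time, appointments, hearing aid fittings, tests" and so on. Table 3 in 3.5.6.3 measures it from a datalog of face-to-face time and of tests, fittings and appointments.

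**Purpose and analysis.** Each arm is introduced as an RCT, the "golden standard for ascertaining the efficacy and safety of a new treatment or intervention". Section 3.5.7 plans analyses of outcome measures only and contains no AE comparison.

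**The concern.** If clients are asked about AEs whenever they are seen, the number of times a client is asked depends on how often that client is seen. Here that number can depend on allocation, through the try-out, app support and, in Arm 2, a hypothesised effect of the app on appointments. The events that the plan anticipates are fatigue and uncomfortable loudness. Both are subjective and can be short-lived, so whether they are recorded may depend on someone asking soon afterwards. No blinding is described that would offset this.

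At stake is the reading of AE frequencies by group. A difference, or the lack of one, could reflect how often clients were asked. This is separate from the question of when the AE reporting window opens and would remain if both groups shared one window.

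**Working it through.** The documents give no figure to reproduce: no AE rate, no contact count by group and no AE test. The calculation below only shows how large the effect could be.

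**Inputs from the documents.** Follow-up is T = 8 weeks in Arms 1 and 3. For Arm 2, T = 6 weeks is used, the upper end of the 4 to 6 weeks of app use in 3.5.6.3. Group sizes are from 3.5.7.1: 75 hearing aid users per group in Arm 1 and 60 in Arm 2.

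**Assumptions.** AEs are equally frequent in both groups and uniform over T. There are k equally spaced contacts after baseline, the last of them at T. An event is captured at the next contact, t weeks later, with probability exp(−t/τ), and there are no spontaneous reports. The recall constant τ runs from 2 to 16 weeks, plus complete recall.

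**Formula.** With L = T/k, the captured share is (τ/L)(1 − exp(−L/τ)).

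Example, T = 8, τ = 4: for k = 1, (4/8)(1 − exp(−2)) = 0.432. For k = 2, (4/4)(1 − exp(−1)) = 0.632. Ratio 0.632/0.432 = 1.46.

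| τ (weeks) | T = 8, 2 v 1 contacts | T = 8, 3 v 2 | T = 6, 3 v 2 |
|---|---|---|---|
| complete recall | 1.00 | 1.00 | 1.00 |
| 16 | 1.12 | 1.04 | 1.03 |
| 8 | 1.24 | 1.08 | 1.06 |
| 4 | 1.46 | 1.15 | 1.12 |
| 2 | 1.76 | 1.28 | 1.22 |

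Each ratio is the group with more contacts over the group with fewer. In Arms 1 and 3, one shared visit follows baseline, so a single extra contact is 2 v 1. In Arm 2, if the first of the three visits is baseline, an extra contact is 3 v 2.

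**Direction.** If app support adds the contact, the ALICE:control ratio exceeds 1. If Arm 2 controls have the additional appointment, it is the inverse. For T = 6 and τ = 2 that is 0.518/0.632 = 0.82, and for τ = 16 it is 0.912/0.940 = 0.97.

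**As counts.** Assume that 20% of clients have an AE.
- Arm 2, 60 × 0.20 = 12 per group, τ = 2, 3 v 2 contacts: 12 × 0.632 = 7.6 recorded against 12 × 0.518 = 6.2.
- Arm 1, 75 × 0.20 = 15 per group, τ = 4, 2 v 1 contacts: 15 × 0.632 = 9.5 against 15 × 0.432 = 6.5.

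These lean towards the high side for a given τ. Equal spacing makes one extra contact count most, and spontaneous reports would narrow the gap.

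**Check on how AEs are then counted.** Take 8 weeks, complete recall, and a week-4 contact in one group only.
- All AEs counted: 8/8 against 8/8, ratio 1.00.
- Only AEs first reported at shared visits: the group with the extra contact keeps 4/8, ratio 0.50.
- AEs elicited by a question covering the whole interval, whether or not reported before: 8/8 against 8/8, ratio 1.00.

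Restricting the count to first reports at scheduled visits would therefore create a bias that the present text does not have.

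**The case against.** The strongest reply is that the protocol already limits the problem. The described visits are the same in both groups. Events reported spontaneously are recorded, and start and stop dates allow an earlier event to be captured at the final visit. The try-out may be extra time within a baseline appointment and not an additional contact. No AE comparison is planned, and the words on safety sit in a general remark about RCTs, while the stated goal of each arm is superiority over standard of care. The loudness event concerns stimuli played by the app, so controls cannot have it, and equal true rates is the wrong premise for that event.

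Most of this stands. A reader might infer that contacts differ by design. The visit text does not support that: the app-only elements are specific, and the Arm 2 reduction is a hypothesis. A reader might also infer that AE counts must differ. They need not, since complete recall at the shared final visit gives 1.00. Nor can one say that the bias favours the app in Arm 2, because app support pulls the other way and the net effect is unknown.

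What remains is that nothing in 3.5.14.3 makes enquiry equal. Spontaneous reporting and dating help only for events that clients remember or volunteer. Fatigue can occur in controls from other causes, so for that event the comparison is meaningful and open to the bias.

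**Conclusion.** The point holds in a limited form. Enquiry is tied to contacts, contacts can differ by group, and recorded AE counts can then differ without an app effect if recall at the shared visits is incomplete. The direction is not determined. The illustrative ratios, 1.00 to 1.76 towards the group asked more often, rest wholly on assumed contact numbers and recall and are not estimates for this trial. The harm is confined to descriptive safety tables and to any safety statement drawn from the randomised comparison. The efficacy analysis is untouched. The change is worth making because it is cheap.

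A larger problem sits beside it. Under Timelines for reporting (3.5.14.3), full AE reporting starts at first use of the device, and before that only procedure-caused AEs are reportable. Controls never use the device, so read literally most of their AEs fall outside reporting.

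**What to change.** In 3.5.14.3:
1. Keep recording every AE whenever it comes to light.
2. At the visits shared by both groups (0 and 8 weeks in Arms 1 and 3, the three visits in Arm 2), put one identical open AE question to every client. It covers the whole period since the previous shared visit, and clients are told to include anything already reported.
3. Flag the source of each AE: shared-visit question, app try-out, app support, other appointment or spontaneous.
4. Base the by-group description on events elicited by the shared question, regardless of any earlier report. Show all AEs alongside.
5. Report contacts per client by group.
6. Reconcile Timelines for reporting so that the window is defined for control clients. Without this, the other steps have little effect.

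The cost is a scripted question at visits that already take place and one extra field on the AE form. Two limits remain. Being asked earlier may itself help a client remember at the shared visit. An event that a client does not repeat there appears only in the table of all AEs.

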#### Mitigation of possible adverse events

The audiometric tests that are used during the study do not contain any risks. The audiometric tests are administered by trained and licenced hearing care professionals in hospitals or hearing centres and are part of the standard of care.

Test sessions of 15 minutes per day are recommended to the participant. It is possible that a participant gets tired within this time. In that case they can take a break or stop the session. Participants are frequently reminded that a session can be paused or stopped at any time. Moreover, each test session is divided into short measurement blocks of 5 minutes. Participants may choose to train longer than the recommended time if they wish but will be informed that the training should be continued the next day after 45 minutes of subsequent training.

